#### 8.3.3.3 EXPECTEDNESS

The study PI will be responsible for determining whether an AE is expected or unexpected. An AE will be considered unexpected if the nature, severity, or frequency of the event is not consistent with the risk information previously described for the study procedures.

---

#### 8.3.4 TIME PERIOD AND FREQUENCY FOR EVENT ASSESSMENT AND FOLLOW-UP

The occurrence of an AE or SAE may come to the attention of study personnel during study visits and interviews of a study participant.

All AEs, not otherwise precluded per the protocol, will be captured on the appropriate eCRF. Information to be collected includes event description, time of onset, clinician's assessment of severity, relationship to study procedures (assessed only by those with the training and authority to make a diagnosis), and time of resolution/stabilization of the event. All AEs occurring while on study will be documented appropriately regardless of relationship. All AEs will be followed to adequate resolution.

Any medical or psychiatric condition that is present at the time that the participant is screened will be considered as baseline and not reported as an AE. However, if the study participant's condition deteriorates at any time during the study, it will be recorded as an AE.

Changes in the severity of an AE will be documented to allow an assessment of the duration of the event at each level of severity to be performed. Documentation of onset and duration of each episode will be maintained for AEs characterized as intermittent.

Study staff will record events with start dates occurring any time after study enrollment until study completion. At each in-person visit or phone call, study staff will inquire about the occurrence of AE/SAEs since the last inquiry. All reported events will be monitored until resolution or study completion. Any reported event that is definitely or probably related to the intervention will be followed until resolution or stabilization.

---

#### 8.3.5 ADVERSE EVENT REPORTING

In consultation with the PI, a trained member of the study team will be responsible for reviewing the AEs with the data safety officer (DSO). Together they will conduct an evaluation of AEs and shall report the results of such evaluation to the reviewing IRB either at the time of continuing review or within 10 working days of becoming aware of the event if the event is considered to be serious or meets the definition of an unanticipated problem involving risks to study subjects or others.

---

#### 8.3.6 SERIOUS ADVERSE EVENT REPORTING

In consultation with the PI, a trained member of the study team will be responsible for reviewing the SAEs with the DSO. The research team member will conduct an evaluation of SAEs and shall report the results of such evaluation to the reviewing IRB as soon as possible, but in no event later than 10 working days after the investigator first learns of the event.

---

#### 8.3.7 REPORTING EVENTS TO PARTICIPANTS

Following review of any AEs/SAEs, the PI will follow the DSO's and IRB's recommended actions. This may include, but is not limited to, modifying the informed consent document or process, re-consenting current participants, providing information to past or current participants (e.g., whenever the information may relate to the participant's willingness to continue), and modifications to the protocol/research plan.

---

#### 8.3.8 EVENTS OF SPECIAL INTEREST

N/A

---

#### 8.3.9 REPORTING OF PREGNANCY

Women who are currently pregnant or planning to become pregnant are not excluded from this study. If any participant becomes pregnant, the participant may remain in the study until study completion.

---

### 8.4 UNANTICIPATED PROBLEMS

---

#### 8.4.1 DEFINITION OF UNANTICIPATED PROBLEMS

This protocol uses the definition of Unanticipated Problems as defined by the Office for Human Research Protections (OHRP). OHRP considers unanticipated problems involving risks to participants or others to include, in general, any incident, experience, or outcome that meets all of the following criteria:

1. Unexpected in terms of nature, severity, or frequency given (a) the research procedures that are described in the protocol-related documents, such as the IRB-approved research protocol and informed consent document; and (b) the characteristics of the participant population being studied;
2. Related or possibly related to participation in the research ("possibly related" means there is a reasonable possibility that the incident, experience, or outcome may have been caused by the procedures involved in the research); and
3. Suggests that the research places participants or others at a greater risk of harm (including physical, psychological, economic, or social harm) than was previously known or recognized.

---

#### 8.4.2 UNANTICIPATED PROBLEMS REPORTING

The PI will report unanticipated problems (UPs) to the reviewing IRB. The UP report will include the following information:

- Protocol identifying information: protocol title and number, PI's name, and the IRB project number.
- A detailed description of the event, incident, experience, or outcome.
- An explanation of the basis for determining that the event, incident, experience, or outcome represents an UP.
- A description of any changes to the protocol or other corrective actions that have been taken or are proposed in response to the UP.

To satisfy the requirement for prompt reporting, UPs will be reported using the following timeline:

- UPs will be reported to the IRB as soon as possible, but no later than 10 working days after the investigator first learns of the event.

#### 8.4.3 REPORTING UNANTICIPATED PROBLEMS TO PARTICIPANTS

Following IRB review of any unanticipated problems, the PI will follow the DSO's and IRB's recommended actions. This may include, but is not limited to, modifying the informed consent document or process, re-consenting current participants, providing information to past or current participants (e.g., whenever the information may relate to the participant's willingness to continue participants), and modifications to the protocol/research plan.

### 9 STATISTICAL CONSIDERATIONS

#### 9.1 STATISTICAL HYPOTHESES

- **Primary Endpoint: Duration of FOG events.**  
We hypothesize that easy to use, accurate, exogenous cueing in response to FOG events will decrease duration of these events.

#### 9.2 SAMPLE SIZE DETERMINATION

The primary outcome measures of the in-community trial of the device will be the duration of freezing events. This will be assessed both with the NFOG-Q and the quantitative data obtained from the device. In a recent trial (CuePed) examining the effects of phasic (intermittent) visual cueing on gait and freezing, Marsh et al. (2019) showed an average 37% decrease in the duration of freezing events with cueing during a 2-minute walk test and a 47% decrease when navigating a freezing provoking environment. The sample size in that study was 20 individuals. Similarly, Ledger et al. (2008) estimated that a clinical trial of auditory cueing for freezing, and gait would require approximately 24 participants per group in order to detect a 20% reduction in freezing at a power level of 80% and a significance threshold of  $p < 0.05$ . Based on these studies we have estimated an effect size of 0.29. To test the primary hypothesis using a repeated-measures ANOVA (two conditions: sham vs. intervention) a sample size of 29 individuals will be required based on  $p < 0.05$ , power = 0.85 and an effect size = 0.29). Assuming a 20% attrition, we plan to recruit 36 individuals for this trial.

#### 9.3 POPULATIONS FOR ANALYSES

N/A

#### 9.4 STATISTICAL ANALYSES

##### 9.4.1 GENERAL APPROACH

Statistical analyses will be performed using the data collected from the insole device. Data from baseline assessments will be summarized and used to describe the population. Discrete variables will be

summarized using frequencies and percentages, while continuous variables will be summarized by means and standard deviations.

---

#### 9.4.2 ANALYSIS OF THE PRIMARY ENDPOINT(S)

The primary outcome measures from this experiment will be the duration of FOG episodes detected by the insole device. A linear mixed effects model (LME, implemented in R) with within-subject factors of intervention (cueing vs. non-cueing) and time (pre vs. post intervention) will be used to test the primary hypothesis. Interaction effects will be tested using Tukey's Honestly Significant (HSD) test. The threshold for significance will be set at the  $p < 0.05$  level. Secondary variables such as the incidence of FOG episodes will be assessed using a Chi-squared analysis.

---

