## 2 INTRODUCTION

### 2.1 BACKGROUND & STUDY RATIONALE

Parkinson's disease (PD) affects more than one million Americans, and its prevalence is expected to double by 2040. Among the most treatment-resistant motor symptoms is freezing of gait (FOG). FOG is defined as “an episodic inability (lasting seconds) to generate effective stepping in the absence of any known cause other than Parkinsonism or high-level gait disorders”. This symptom affects more than 30% of all participants with PD and is characterized by episodic impairments in the ability to initiate gait and the spontaneous arrest of movement during stepping. Incidence of FOG increases with severity and duration of PD with 80% of severely affected participants reporting freezing. Episodes last from a few seconds to up to one minute and can be triggered by turning, approaching a narrow doorway or obstacles, or seemingly nothing in particular. The incidence and severity of FOG episodes increases with disease progression. While levodopa and deep brain stimulation can often reduce the incidence and duration of FOG episodes, the efficacy of these treatments generally decreases over time.

Clinicians have long recognized that one of the best methods to facilitate movement initiation in participants with PD is to provide them with a sensory cue (e.g., visual, acoustic, or somatosensory). Performance following a cue is often equivalent to, or greater than, that observed with levodopa replacement therapy. Existing products that provide cueing such as the LaserCane either use a continuous signal or periodic metronome-like signal, however, their effectiveness diminishes quickly over time. It has recently been shown that the reliability and effectiveness of external cueing is critically dependent upon the timing and method of presentation of the stimulus. If the external stimulus is self-triggered (e.g., via button press, as is done in most commercially available cueing systems), the cue is ineffective in improving gait initiation. If the cue is exogenously presented, the incidence of an inappropriate gait initiation sequences is reduced from 20% to less than 1% and the magnitude of force generation during stepping increases by an average of 45-71%.

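### Section 9.4.2 leaves the unit of analysis, random effects and scale of the primary mixed model open, and read plainly it does not use the person-level error term behind N = 29

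*Combined protocol and SAP*

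**What the plan says.** Section 9.4.2 defines the outcome: "The primary outcome measures from this experiment will be the duration of FOG episodes detected by the insole device". The model is "A linear mixed effects model (LME, implemented in R) with within-subject factors of intervention (cueing vs. non-cueing) and time (pre vs. post intervention", and on the error rate it says "The threshold for significance will be set at the" 0.05 level. It does not say whether a row is one episode or one summary per participant and phase. It gives no random effects, transformation or degrees-of-freedom method. Section 9.3 (populations) is marked not applicable, and section 9.4.1 adds only means and standard deviations for continuous variables.

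Section 9.2 sizes the trial by "repeated-measures ANOVA (two conditions: sham vs. intervention", with "power = 0.85 and an effect size = 0.29", and concludes that "a sample size of 29 individuals will be required based on" those inputs. That calculation takes one value per person per condition.

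Section 6.1.2 sets three recording periods: 7 days with cueing off, 21 days on, 7 days off. On the distribution of durations, section 2.1 offers only "Episodes last from a few seconds to up to one minute". On the expected effect, section 9.2 cites a trial that "showed an average 37% decrease in the duration of freezing events with cueing" in a 2-minute walk test, and 47% in a freezing-provoking setting.

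**The concern.** Thirty-five days of recording may yield many episodes per person. Two sources of scatter then bear on the comparison of cueing with no cueing: scatter between episodes of one person in one phase, and differences between people in how far their typical duration shifts from phase to phase. The repeated-measures calculation in section 9.2 uses the second as its error. An episode-level model with only a participant intercept uses the first, and so counts each further episode as fresh evidence about the average effect, although it comes from the same people. If people differ in their shift, the stated precision is too high and a test set at 5% rejects more often than that.

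The trial is unblinded, has one arm and rests on this comparison. Leaving the error term and the scale open lets the p-value depend on choices made after the data are seen.

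The scale is a separate matter. It decides how much a few very long episodes weigh, and whether the effect is a difference in seconds or a ratio.

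**Working it through.** **1. The plan's own figure.** For a within-subject ANOVA with m = 2 conditions, λ = f²·N·m/(1−ρ), on 1 and N−1 degrees of freedom. The plan gives effect size 0.29, alpha 0.05 and power 0.85. It does not name the metric or give a correlation, so Cohen's f and ρ = 0.5 are assumptions.
- N = 29: λ = 0.29² × 29 × 2 / 0.5 = 9.756, power 0.854.
- N = 28: λ = 9.419, power 0.841.

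So N = 29 reproduces. It would be 56 at ρ = 0, 40 at ρ = 0.3 and 19 at ρ = 0.7. Read as a paired standardised difference, 0.29 would need 109 people (two-sided). The match is therefore to a test with the person as unit. With 36 recruited and 20% attrition, 36 × 0.8 = 28.8 are expected to complete.

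**2. Error left out by an intercept-only episode model.** Let σ be the log-SD between episodes of one person in one phase, τ the log-SD across people of the off-to-on shift, and k the episodes in the off week, with 3k over the three on weeks. The variance of one person's phase difference is σ²(1/k + 1/(3k)) + τ². The intercept-only model omits τ², so approximately

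R = true SE / reported SE = √[1 + (τ²/σ²) / (1/k + 1/(3k))], and type I error = 2[1 − Φ(1.96/R)].

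The number of people cancels. Example: σ = 0.8, τ = 0.25, k = 20 gives τ²/σ² = 0.0977 and 1/20 + 1/60 = 0.0667, so R = √(1 + 1.465) = 1.570, 1.96/R = 1.248, and type I error is 21%.

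σ, τ and k are all assumed. With σ = 0.8 and equal counts in everyone:

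| τ | k = 5 | k = 20 | k = 50 |
|---|---|---|---|
| 0.10 | 5.7% | 7.8% | 12.0% |
| 0.20 | 7.8% | 15.9% | 28.4% |
| 0.25 | 9.4% | 21.2% | 36.4% |

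**3. Simulation under no average effect (29 people, lognormal durations, σ = 0.8).**
- τ = 0 to 0.1 with few episodes: 4–7%.
- τ = 0.25, 20 a week: 23–31% in one set of runs and 35% in another, whose counts differ strongly between people (log-SD 1.0). Wider variations of scale, count inequality and where the random effect enters gave 17–46%.
- τ = 0.25, 50 a week: 38–47%.
- Person-level tests in the same runs as the 4–7%, 23–31% and 38–47% figures: 3–6%.
- Fitted mixed models, τ = 0.2, 10 and 20 a week: 12% and 14% with a participant intercept only, 4% and 5% with a random phase slope. These rest on 150 runs each, some with convergence warnings, so they are approximate.

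**4. Skew on its own.** With τ = 0 and skewed raw seconds, the common-slope test rejects 4.3–7.2% (Monte Carlo error about 0.9 points). With τ = 0.2 it rejects 9–31% on raw seconds and 9–39% on logs. Skew does not cause the inflation and a log scale does not cure it.

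**5. What the scale changes.** At 20 episodes a week, simulated power for log versus raw seconds was 73% against 54% in one set of runs (a 20% reduction, person-level test) and 78% against 55% in another. At 7 a week it was 47% against 29%. The data were generated as lognormal, and the 20% reduction is proportional, which favours the log scale by construction.

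**The case against.** The strongest reply is that the plan is silent, not wrong. A reader might infer that it specifies raw seconds, excludes a person-specific phase effect, and so produces p-values that are too small. The text does not support that. A mixed model with within-subject factors already contains the participant. It is compatible with participant-by-phase summaries, a log scale or a random phase slope, and the section 9.2 calculation points to the person as unit. This stands, and it is why the point concerns what is left open and what the plain reading would do. It does not remove the point, because nothing in section 9.4.2 commits the analyst to any of these.

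A reader might also infer that skew drives the small p-values. Step 4 shows otherwise.

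The sizes are conditional. With few episodes or little variation between people the inflation is negligible: 5.4% at τ²/σ² = 0.01 with 5 episodes in the off week. The higher simulated figures also depend on how unequal the episode counts are.

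Nor is every effect that the plan cites a proportional change in duration. The 0.29 is unitless, and the 20% figure in section 9.2 concerns freezing generally. Only the 37% and 47% figures are percentage reductions in duration, and averages of that kind do not establish a multiplicative effect in each person. The case for logs is therefore one of plausibility and robustness.

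**Conclusion.** The point holds as a gap in specification with a conditional consequence. Fitted to single episodes with a participant intercept only, the model would overstate precision relative to the 29-person calculation whenever the phase effect differs between people. At an assumed residual log-SD of 0.8, the type I error is close to 5% with few episodes and a phase log-SD up to 0.1. At 0.25 it is about 20–35% with 20 episodes a week and about 40–50% with 50 (36% by the equal-count formula), against about 3–6% with a person-level error term. The documents supply none of these variances or counts, so the range matters more than any single figure in it.

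The question of scale is secondary and separate. Logs would probably be more efficient and less sensitive to long episodes, but they do not correct the error rate. The plan should be amended on both before the data are analysed.

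**What to change.** In section 9.4.2, state that the primary analysis is a linear mixed model on log(duration), one row per episode, with:
- phase (off, on, off) as a fixed factor, naming the phase contrast that tests the hypothesis;
- a random participant intercept and a random participant-by-phase effect;
- small-sample degrees of freedom at person level, for example Kenward-Roger or Satterthwaite.

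Report the ratio of geometric mean durations with its 95% confidence interval, and median durations in seconds as description.

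A paired analysis of each person's mean log duration per phase is a valid and simpler alternative or sensitivity analysis. It is not identical to the mixed model when episode counts differ. With counts varying between people at log-SD 1.0, the unweighted paired mean has about 26–44% more variance at 20 a week (phase log-SD 0.25) and about 70–90% more at 7 a week (phase log-SD 0.15).

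The cost is wording only, and N = 29 is unchanged because it already assumes a person-level contrast. The downside is that the effect is reported as a ratio and the interval is wider than the intercept-only one.

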## 3 OBJECTIVES AND ENDPOINTS

OBJECTIVES	ENDPOINTS
Primary	
Aim 3 : To validate the haptic module and insole device system and evaluate its efficacy with an in-community clinical trial.	Duration of FOG events.

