#### 6.1.2 ADMINISTRATION AND/OR DOSING

The main purpose of this study is to establish the robustness and efficacy of the haptic module and insole device through long-term, continuous use while subjects proceed with their activities of daily living at home and in the community. Data will be collected in three parts. Part 1 will collect data for 7 days with the cueing intervention turned off to establish a baseline. Part 2 will collect data over 21 days with the cueing intervention turned on. Part 3 will examine the wash-out effects of cueing by collecting for an additional 7 days with the cueing intervention turned off. Throughout this trial, daily dairies of FOG episodes, user impressions, and adverse events will be collected. Data from the insole will automatically (no participant interaction for the duration of the study) be downloaded by the charging mat's nRF52840

BLE radio/processor and stored to a secure digital card. Participants will be contacted weekly by the research coordinator to discuss use of the device and compliance with protocol.

The sensing device consists of two parts for each leg: the Haptic Module and the Insole (Figure 1). The Haptic Module wraps around the lower leg (Figure 2) of the user and contains electronics for wireless communication, a microprocessor, and four vibrating motors that provide gentle tactile sensory cues to the front, back, medial, and lateral surfaces of the user's leg when a FOG event is detected. The Haptic Module has a power button, two status LEDs, and a reset button. Power is supplied by a rechargeable internal battery.

The Insole is a pressure-sensitive insert that fits in a regular shoe with a battery and electronics for sampling pressure measurements. The electronics are housed in a sealed plastic case that securely clips to the outside of the wearer's shoe (Figure 2). The insole has a single status light and no buttons. Users recharge the insole and haptics module via USB connectors.

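### Detected-episode duration exists only where an episode is detected, and with no merging rule a freeze broken in two by the cue can lower it without reducing time frozen

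*Combined protocol and SAP*

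**What the plan says.** Section 3 gives a single endpoint, "Duration of FOG events". Section 9.4.2 makes it operational: "The primary outcome measures from this experiment will be the duration of FOG episodes detected by the insole device". The test is a linear mixed effects model whose "within-subject factors of intervention (cueing vs. non-cueing) and time (pre vs. post intervention) will be used to test the primary hypothesis". The plan does not say whether the unit is the single episode or a participant summary, and it names no summary measure.

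Section 9.2 adds a second source: "This will be assessed both with the NFOG-Q and the quantitative data obtained from the device". Section 9.4.2 uses the device alone.

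Episode number appears once: "Secondary variables such as the incidence of FOG episodes will be assessed using a Chi-squared analysis". Section 9.4.3, for secondary endpoints, is marked not applicable.

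Under section 6.1.2 the motors vibrate "when a FOG event is detected", so the cue arrives in an event that has already begun. The same section sets the phases: "Part 1 will collect data for 7 days with the cueing intervention turned off to establish a baseline", then 21 days with cueing on and 7 days with it off. Section 6.1.1 asks for as much wear as participants can manage and sets no hours.

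The documents give no minimum episode length, no gap rule for joining close detections, no handling of phases without an episode, and no measure of total or per-hour frozen time.

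**The concern.** The number and mix of detected episodes can change with cueing, and a duration measured per episode changes with them.

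The direct route is fragmentation. The cue releases the person for a moment, they freeze again, and the device logs two short events where there would have been one long one. Without a gap rule fixed in advance, the choice between one event and two is left open until the data are in hand. This error favours the device, in a study that section 4.1 describes as unblinded, uncontrolled and single-arm.

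The second problem is missing zeros. A participant with no detected episode in a phase contributes no duration to that phase, although no freezing is the best possible result. Inclusion requires evidence of freezing but no minimum frequency, so an empty 7-day phase is possible.

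At stake is whether a fall in the primary outcome can be read as less time frozen.

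**Working it through.** **1. The plan's own figure.** Inputs from section 9.2: effect size 0.29, power 0.85, significance level 0.05, two conditions, 20% attrition. The type of effect size and the within-person correlation are not stated; I take 0.29 as Cohen's f and assume a correlation of 0.5.

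- Noncentrality = f² × n × m / (1 − ρ) = 0.29² × 29 × 2 / 0.5 = 9.76, with 1 and 28 degrees of freedom.
- Power is 0.854 at n = 29, so the stated 29 reproduces.
- 29 / 0.8 = 36.25 against the stated 36. The difference is immaterial (36 × 0.8 = 28.8; power at 28 is 0.841).

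The point below concerns what the endpoint measures. It leaves the sample size untouched.

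**2. Effect of splitting.** Mean duration = total frozen time / number of episodes = T/N. If a share q of episodes is each logged as two and T is unchanged, N becomes N(1+q), and the mean is multiplied by 1/(1+q).

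| Share split (assumed) | Multiplier | Fall in mean duration | Change in time frozen |
|---|---|---|---|
| 25% | 1/1.25 = 0.80 | 20% | 0% |
| 59% | 1/1.59 = 0.63 | 37% | 0% |
| 89% | 1/1.89 = 0.53 | 47% | 0% |

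The 37% and 47% rows match the reductions that section 9.2 cites from the visual-cueing trial (2-minute walk and freezing-provoking environment).

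**3. A mixed set of episodes.** Assumed durations: 60 of 2 s, 30 of 10 s and 10 of 30 s. Total = 120 + 300 + 300 = 720 s; mean = 720/100 = 7.2 s.

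- Every episode of 10 s or more split in two: 60 + 80 = 140 episodes, still 720 s. The mean is 5.14 s, down 28.6%; time frozen is unchanged.
- Half of the 2 s episodes prevented: 70 episodes, 660 s. The mean is 9.43 s, up 31.0%; time frozen is down 8.3%.
- A random half of all episodes prevented: the mean is unchanged; time frozen is down 50%.

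The sizes depend on the assumed durations. That duration and time frozen can separate does not.

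**4. Do other planned analyses catch it?**

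- Incidence: splitting raises counts, so it would leave a trace. But the chi-squared analysis has no exposure denominator, the phases last 7, 21 and 7 days, and wear is not fixed. A higher raw count in the cued phase is expected from its length alone.
- NFOG-Q: the schedule of activities places it at the pre- and post-treatment visits only, so it cannot compare phases.
- FOG diary: collected daily, but section 9 gives it no analysis, and section 9.4.1 bases the analyses on device data.

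No sample size for frozen time per hour can be computed, because the documents give no mean, variance or episode count for it.

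**The case against.** The strongest reply is that the endpoint fits the hypothesis. Sections 4.1 and 9.1 predict that cueing in response to a freeze will shorten it, the title speaks of release, and the cue acts only after detection. Duration given an event is the intended target; total frozen time is a broader question. This stands, and it is why duration should remain primary.

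Next, incidence is planned, so heavy splitting would show as more events. This stands in part: the information would exist, but the named test has no wear denominator and nothing joins it to duration.

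Third, refining the algorithm is Aim 2 and this protocol covers Aim 3 in the community, so an episode definition may sit in algorithm documents outside this one. That is possible. The plan would then need only to cite the rule and fix it for all phases.

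A reader might also infer that prevention of short freezes inflates the apparent benefit. It does not. A cue cannot prevent the freeze that triggered it, so prevention would need carry-over, learning or cues from false detections. Where short freezes are the ones prevented, mean duration rises, which counts against the device.

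**Conclusion.** The concern holds as a gap in definition and a missing supportive analysis. The primary outcome is conditional on a detected episode, the cue acts inside the interval being timed, and no stated rule prevents one interrupted freeze from counting as two. With time frozen unchanged, splitting 25% of episodes gives a 20% fall in mean duration, and 59% gives a fall as large as the 37% cited in section 9.2. This rests on assumed split shares and on a mean as the summary; the plan names no summary, but single-episode and participant-level analyses share the conditioning. Only a reading as summed duration would escape it, and section 9.4.2 does not support that reading.

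Three stronger readings are tempting and unsupported:

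- That an observed fall would be an artefact. The documents contain no data on re-freezing or on how often phases are empty.
- That the primary endpoint should be replaced. It matches the stated hypothesis.
- That efficacy should be claimed only if frozen time moves in the same direction as duration. Such a gate does not do its job. If 10 freezes of 12 s became 20 of 5 s, mean duration would fall 58% (12 to 5 s) and total time 17% (120 to 100 s). Both fall, so the gate passes although most of the apparent gain is fragmentation.

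**What to change.** Keep duration as primary and change the statistical section as follows.

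1. State one episode definition and one gap for merging consecutive detections. Fix both before data are examined and apply them identically in all phases. If they already exist in algorithm documents, cite them. State the unit of analysis.
2. Add a supportive analysis of total detected frozen time per hour of wear, per participant and phase, using the same cueing-on versus cueing-off contrast. Report it with its confidence interval beside the duration result.
3. Include zeros for phases with wear and no episode. Treat a phase without wear as missing, not zero; section 6.1.1 allows for unworn weeks 1 and 5 if remote switching fails.
4. Derive wear time from the insole data that section 6.1.2 says are downloaded automatically, and state the derivation and non-wear rule. Section 8.1 records daily use only through the weekly call.
5. Say that a fall in duration without a fall in frozen time per hour will be interpreted as possible fragmentation. Do not add a direction-only gate.

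Cost: a wear-time derivation and one extra model, with no new visits or participants. Downsides: frozen time per hour also depends on how much worn time is spent walking, and it includes false detections (Phase I specificity 92%, section 4.3). A benefit seen in duration alone would be reported more cautiously.
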